1 PROTOCOL SUMMARY

Background and Rationale

This study is designed to evaluate the gingivitis efficacy of twice daily brushing with a 0.454% stannous fluoride (SnF₂) dentifrice over 3 weeks in a population with mild-moderate plaque-induced gingivitis. The study will compare a marketed dentifrice containing 0.454% SnF₂ with a negative control dentifrice. The design of this study follows very closely that of previous GSK CH gingivitis studies ([Parkinson et al, 2014](#); [Parkinson et al, 2015](#); [Parkinson et al, 2018a](#); [Parkinson et al, 2018b](#))

Objectives and Endpoints

Objective(s)	Endpoint(s)
Primary	
To evaluate the clinical efficacy of a 0.454% SnF ₂ dentifrice in reducing gingivitis (following dental prophylaxis), as measured by the Bleeding Index (BI), compared to a negative control dentifrice, when used twice daily for 3 weeks.	Mean BI at Week 3
Secondary	
To evaluate the clinical efficacy of a 0.454% SnF ₂ dentifrice in reducing gingivitis (following dental prophylaxis), as measured by the BI compared to a negative control dentifrice, when used twice daily for 2 weeks.	Mean BI at Week 2
To evaluate the clinical efficacy of a 0.454% SnF ₂ dentifrice in reducing gingivitis (following dental prophylaxis), as measured by the number of bleeding sites (NBS), compared to a negative control dentifrice, when used twice daily for 2 and 3 weeks.	Mean NBS at Week 2 and Week 3
To evaluate the clinical efficacy of a 0.454% SnF ₂ dentifrice in reducing gingival inflammation (following dental prophylaxis), as measured by the Modified Gingival Index (MGI), compared to a negative control dentifrice, when used twice daily for 2 and 3 weeks.	Mean MGI at Week 2 and Week 3
To evaluate the clinical efficacy of a 0.454% SnF ₂ dentifrice in reducing supra – gingival plaque formation (following dental prophylaxis) as measured by the Turesky modification of the Quigley & Hein plaque index (TPI), compared to a negative control dentifrice, when used twice daily for 2 and 3 weeks.	Mean TPI (overall and interproximal) at Week 2 and Week 3
Safety	
To assess the safety and tolerability of a 0.454% SnF ₂ dentifrice when used twice daily over 3 weeks.	Treatment emergent adverse events

Study Design

This will be a single center, controlled, single blind (examiner blind), randomized, stratified (gender and baseline mean whole mouth MGI score) two-treatment arm, parallel design, clinical study. Study subjects will be aged 18-65 years, non-smokers, in good general health with generalized mild-moderate plaque-induced gingivitis and ≥ 20 natural teeth that meet all study criteria at both the Screening and Baseline visits (including ≥ 40 evaluable surfaces for MGI, BI, and TPI).

Approximately 130 (n=65/group) subjects will be randomized to one of the study products.

This study will consist of four study visits. At Visit 1, Screening, after signing informed consent, subjects will undergo an Oral Soft Tissue (OST) examination, an Oral Hard Tissue (OHT) examination and a gross assessment of gingival health, in addition to the standard (inclusion, exclusion, medical history, demographics, prior/current medications) procedures to assess eligibility for the study. Subjects will return to site 1-28 days after the Screening Visit, for Visit 2, Baseline.

At the Baseline Visit, subjects will undergo, in the following order, a full OST examination followed by assessments of gingival inflammation (MGI), gingival bleeding (BI) and supra-gingival plaque using the Turesky Plaque Index (TPI). Eligible subjects will be stratified based on gender and baseline mean whole mouth MGI score (Low: ≤ 2.00 /High >2.00), to ensure a balance of gingivitis across both treatment groups and then randomized to study product.

Subjects with mean MGI or TPI scores outside the study range will be discontinued from the study at this visit. To control inter-examiner variability, the same examiner will be used throughout the study for all clinical assessments (MGI, TPI, BI).

All randomized subjects will then receive a full mouth dental prophylaxis (followed by flossing) to remove sub and supra-gingival calculus, stain, plaque and debris from the teeth. All subjects will enter the treatment period with no visible plaque (TPI=0).

After all clinical assessments, subjects will be instructed to brush for 1 timed minute, in their usual manner, with their assigned study product and then instructed to continue using their assigned product twice daily (morning and evening), after which they will return to site for their Week 2 (Visit 3) assessments. Subjects will then continue using their assigned dentifrice for a further week, after which they will return for their Week 3 (Visit 4) assessments. Subjects will continue to record all brushing events in the diary provided, and this will be reviewed by the site at each study visit.

After the Week 3 visit, study closeout procedures (return of study product etc.) will take place and the subject may undergo an additional prophylaxis if it is deemed necessary by the examiner.

Safety and oral tolerability of the study products will be monitored over the 3-week treatment period by review of reported Adverse Events and Incidents.

Study Products

Test dentifrice: Sensodyne Repair and Protect containing 0.454% SnF₂ (1100 parts per million(ppm) fluoride)

Negative control dentifrice: Colgate Cavity Protection (1100ppm fluoride as sodium monofluorophosphate (SMFP)).

Type and Planned Number of Subjects

Approximately 150 subjects will be screened to randomize 130 to ensure 60 evaluable subjects per treatment group complete the entire study.

Statistical Analysis

The primary variable is the mean BI at week 3.

The mean BI score will be analyzed using ANCOVA with treatment group, gender, and baseline MGI stratification (low/high) as factors and baseline score as a covariate. Adjusted means of the two treatments and treatment difference will be provided together with 95% CIs and P-values.

Secondary variables are: -

Mean BI at week 2

Mean NBS at week 2 and 3

Mean MGI at week 2 and 3

Mean TPI (Overall) at week 2 and 3

Mean TPI (Interproximal areas) at week 2 and 3

Each secondary variable will be analyzed separately as per the primary variable. For the analysis of MGI the stratification factor of MGI will not be included as the baseline value of MGI is included as a covariate.

1.1 Schedule of Activities

The schedule of activities table provides an overview of the subject visits and study procedures.

The investigator may schedule visits (unplanned visits) in addition to those listed on the schedule of activities, to conduct evaluations or assessments required to protect the well-being of the subject.

Table 1-1 Schedule of Activities

Procedure/Assessment	Visit 1 Screening		Visit 2 Day 0 Baseline	Visit 3 Week 2 (14± 2 days post V2)	Visit 4 Week 3 (21± 2 days post V3)	
Informed consent	X	Lead-in Phase Minimum 1 day - Maximum 28 days				
Demographics	X					
Medical history	X					
Prior/current medications and treatments	X					
OST assessment	X			X	X	
OHT assessment	X				X	
Gross assessment of gingival health ¹	X					
Inclusion/Exclusion criteria	X			X		
Subject Eligibility	X			X		
Subject continuance					X	X
Concomitant medications and treatments				X	X	X
MGI assessment				X	X	X
Repeat MGI Assessment ²				X	X	X
BI assessment				X	X	X
Disclose dental plaque				X	X	X
TPI Assessment				X	X	X
Repeat TPI Assessment ²				X	X	X
Stratification/Randomization				X		
Dental Prophylaxis				X		
Post-prophylaxis examination to confirm whole mouth TPI=0				X		
Dispense study product, toothbrush and diary				X		
Supervised brushing with study product				X	X	
Subject brings study product, toothbrush and completed diary to site for compliance check ³					X	X
Subject returns study product and diary to site						X
End of study dental prophylaxis (optional)						X
Adverse events/incidents ⁴	X			X	X	X
Study conclusion						X

Abbreviations:

OST Oral soft tissue

OHT Oral hard tissue
MGI Modified gingival index
BI Bleeding index
TPI Turesky plaque index

Footnotes:

1. Subjects with generalized mild-moderate gingivitis, as determined by visual assessment of gingival health, will continue in the study.
2. At least 2 repeatability assessments should be performed each day (≥ 1 in the morning; ≥ 1 in the afternoon)
3. Visits 2-4: Adherence to Lifestyle Guidelines/Medication Requirements;
Visits 3-4: Compliance with use of study product (visual check if returned study supplies/review of diary)
4. Adverse events (AEs)/incidents will be recorded from the signing of informed consent until 5 days after the last dose of study product.

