2.1 Study Rationale

This study will compare a 0.454% SnF₂ dentifrice (Sensodyne Repair and Protect) versus a negative control dentifrice. The aim of this study is to evaluate the gum health efficacy of twice daily brushing with a 0.454% SnF₂ dentifrice over 3 weeks.

Several GSK CH studies (Parkinson et al, 2014; Parkinson et al, 2015; Parkinson et al, 2018a; Parkinson et al, 2018b) have previously investigated the gingival health benefits of SnF₂ at timepoints ranging from 4 to 24 weeks, but to date there have been no GSK CH studies that have looked at timepoints earlier than 4 weeks for this stabilized anhydrous 0.454% SnF₂ dentifrice. There is a desire to show an improvement in gum health at earlier timepoints than 4 weeks and it is believed that recordable gum health benefits may be feasible after 2 to 3 weeks of use (Löe et al, 1965). Therefore, this study is planned to investigate the efficacy of the dentifrice at reducing gingivitis and plaque at the earlier time points of 2 and 3 weeks.

As per the above-mentioned GSK CH studies, the main gingivitis indices that will be employed in this study will be the Bleeding Index (BI), number of bleeding sites (NBS), Modified Gingival Index (MGI) and the Turesky Plaque Index (TPI). This will be a parallel study design that will require subjects to use their assigned dentifrice twice daily for a maximum of 3 weeks, with measurements taken at 2 and 3 weeks.

This is a Phase IV study that is planned to be performed by a clinical site with experience in the above-mentioned gingivitis indices, and therefore a study site in the USA has been selected.

Complete information for the Sensodyne Repair and Protect dentifrice may be found in the single reference safety document (SRSD), which for this study is the Investigator Brochure.

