4 STUDY DESIGN

4.1 Overall Design

This will be a single center, controlled, single blind (examiner blind), randomized, stratified (gender and baseline mean whole mouth MGI score) two-treatment arm, parallel design, clinical study. Study subjects will be aged 18-65 years, non-smokers in good general health with generalized mild-moderate plaque-induced gingivitis and ≥ 20 natural teeth that meet all study criteria at both the Screening and Baseline visits (including ≥ 40 evaluable surfaces for MGI, BI, and TPI).

Approximately 130 (n=65/group) subjects will be randomized to one of the study products.

This study consists of 4 study visits. At Visit 1, Screening, after signing informed consent, subjects will be assessed for eligibility based on the inclusion/exclusion criteria and will undergo Oral Soft and Hard Tissue (OST, OHT) assessments.

Subjects will return between 1 and 28 days following the Screening Visit for the Visit 2, Baseline where they will undergo, in the following order, a full OST examination followed by assessments of gingival inflammation (MGI), gingival bleeding (BI) and supra-gingival plaque (TPI). Eligible subjects will be stratified based on gender and baseline mean whole mouth MGI score (Low: ≤ 2.00 /High > 2.00), to ensure a balance of gingivitis across both treatment groups and then randomized to study product.

All randomized subjects will receive full mouth dental prophylaxis (followed by flossing) to remove sub and supra-gingival calculus, stain, plaque and debris from the teeth. All subjects will enter the treatment period with no visible plaque (TPI=0). After all clinical assessments, subjects will be instructed to brush for 1 timed minute at site with their assigned study product, after which they will be instructed to continue using this twice daily (morning and evening) for 2 weeks. After 2 weeks they will return to site for their Week 2 (Visit 3) assessments. They will then continue using their test dentifrice for a further week and will continue to record all brushing events in the diary provided, after which they will return for their Week 3 (Visit 4) assessments. All assessments will be carried out on the facial and lingual/palatal surfaces of each incisor, canine, pre-molar and molar, excluding third molars. To control inter-examiner variability, the same examiner will be used throughout the study for each clinical index.

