8 STUDY PROCEDURES

This section lists the procedures to be completed at each planned study visit. The timing of each procedure is listed in the [Schedule of Activities](#), Section 1.1.

Adherence to the study design requirements, including all procedures are essential and required for study conduct.

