8.2.3 Visit 4 /Day 21 (Week 3)

The following procedures/ assessments will take place in the order listed below as much as possible and recorded in the eCRF:

- Collect study dentifrice, toothbrush, diary & timer (all study supplies) from subject.
- Review of concomitant medications and non-drug treatments/ procedures, adverse events, incidents and lifestyle restrictions.
- Compliance checks including diary review.

- Subject eligibility / continuance.
- Full **OHT examination** (Section 9.1.1).
- Full **OST examination** (Section 9.1.2).
- **MGI assessment** (& repeatability assessment, where applicable) (Section (9.2.1)).
- **BI assessment** (Section 9.2.2).
- **Plaque disclosure** (Section 9.2.3).
- **TPI assessment** (& repeatability assessment, where applicable) (Section 9.2.4).
- End of study dental prophylaxis (optional - if deemed necessary by examiner).
- **Adverse events & Incidents** (Section 10).
- Study conclusion

Changes in concomitant medication or non-drug treatments/procedures will be documented in the eCRF.

Spontaneous reporting of adverse events and those elicited by asking subjects to respond to a non-leading question such as “How do you feel?” will be assessed and any AEs recorded in the eCRF.

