1.1 Study Design

This will be a single center, controlled, single blind (examiner blind), randomized, stratified (gender and baseline mean whole mouth Modified Gingival Index [MGI] score), two-treatment arm, parallel design, clinical study. Study subjects will be aged 18-65 years, non-smokers, in good general health with generalized mild to moderate plaque-induced gingivitis and ≥ 20 natural teeth that meet all study criteria at both the Screening and Baseline visits, including ≥ 40 evaluable surfaces for MGI, BI, and Turesky Plaque Index (TPI).

Approximately 130 (n=65/group) subjects will be randomized to one of the study products.

The schedule of activities in [Table 1-1](#) provides an overview of the subject visits and study procedures. The investigator may schedule visits (unplanned visits) in addition to those listed on the schedule of activities, in order to conduct evaluations or assessments required to protect the well-being of the subject.

Table 1-1 Schedule of Activities

Procedure/Assessment	Visit 1 Screening		Visit 2 Day 0 Baseline	Visit 3 Week 2 (14± 2 days post V2)	Visit 4 Week 3 (21± 2 days post V2)
Informed consent	X	Lead in Phase Minimum 1 day - Maximum 28 days			
Demographics	X				
Medical history	X				
Prior/current medications and treatments	X				
OST assessment	X		X	X	X
OHT assessment	X				X
Gross assessment of gingival health ¹	X				
Inclusion/Exclusion criteria	X		X		
Subject Eligibility	X		X		
Subject continuance				X	X
Concomitant medications and treatments			X	X	X
MGI assessment			X	X	X
Repeat MGI Assessment ²			X	X	X
BI assessment			X	X	X
Disclose dental plaque			X	X	X
TPI Assessment			X	X	X
Repeat TPI Assessment ²			X	X	X
Stratification/Randomization			X		
Dental Prophylaxis			X		
Post-prophylaxis examination to confirm whole mouth TPI=0			X		
Dispense study product, toothbrush and diary			X		
Supervised brushing with study product			X	X	
Subject brings study product, toothbrush and completed diary to site for compliance check ³				X	X
Subject returns study product and diary to site					X
End of study dental prophylaxis (optional)					X
Adverse events/incidents ⁴	X		X	X	X
Study conclusion					X

Abbreviations: OST = Oral soft tissue, OHT = Oral hard tissue, MGI = Modified gingival index, BI = Bleeding index, TPI = Turesky plaque index

Footnotes:

- Subjects with generalized mild-moderate gingivitis, as determined by visual assessment of gingival health, will continue in the study.

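### Protocol Table 1-1 counts the Week 3 primary-endpoint visit from Visit 3 instead of Visit 2, which read literally puts it at Day 31–39 rather than Day 19–23

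*Protocol*

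**What the plan says.** Protocol section 1.1, Table 1-1, labels Visit 4 as Week 3 and gives its window as "21± 2 days post V3". The neighbouring Visit 3 column is counted from Visit 2, at 14 ± 2 days. Section 8 makes the table operative for scheduling: "The timing of each procedure is listed in the" Schedule of Activities.

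Elsewhere, both documents put Visit 4 about three weeks after baseline:

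- SAP section 1.1, Table 1-1, prints the same column as "21± 2 days post V2".
- Protocol section 8.2.3 is headed with Day 21 and Week 3.
- The protocol summary says that after the Week 2 visit subjects "continue using their assigned dentifrice for a further week" before returning for Visit 4. Section 4.1 says the same: "They will then continue using their test dentifrice for a further week".
- Protocol section 2.1 has subjects "use their assigned dentifrice twice daily for a maximum of 3 weeks".

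The primary efficacy variable, and the only success criterion, is mean Bleeding Index (BI) at Week 3 (protocol sections 3 and 12.2.5).

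**The concern.** A visit 21 days after the Week 2 visit falls at about Week 5, so the header contradicts its own Week 3 label. Visit 4 is where the primary endpoint is measured, and this header is the only place in the protocol that gives a ± tolerance for it; section 8.2.3 gives only a nominal day. A coordinator who needs the permitted range has to take it from the wrong cell.

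Two things would follow from using the table as printed:

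- **Timing of the endpoint.** The assessment would be made about two weeks late. Section 2.1 justifies the trial on the ground that there have been "no GSK CH studies that have looked at timepoints earlier than 4 weeks" for this formulation. A visit in the printed window would fall after four weeks, and product use would exceed the three-week maximum.
- **Deviation logging.** Against the printed window, a visit made correctly on Day 21 is out of window. SAP section 4.1.2 lists visit-window violations among the possible important deviations, and the protocol and SAP give windows for this visit that do not overlap.

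**Working it through.** The check is date arithmetic, with baseline (Visit 2) as Day 0, as in Table 1-1.

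**Inputs**

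| Quantity | Value | Source |
|---|---|---|
| Visit 3 window | 14 ± 2 days after Visit 2 | Protocol Table 1-1 |
| Visit 4 window, as printed | 21 ± 2 days after Visit 3 | Protocol Table 1-1 |
| Visit 4 window, SAP | 21 ± 2 days after Visit 2 | SAP Table 1-1 |
| Visit 4 nominal day | Day 21 | Protocol section 8.2.3 |

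**Step 1. Visit 3.** 14 − 2 = 12 and 14 + 2 = 16, so Day 12–16.

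**Step 2. Visit 4 as printed.** This is the Visit 3 day plus 19 to 23 days.
- Earliest: 12 + 19 = Day 31 (31/7 = 4.43 weeks)
- Latest: 16 + 23 = Day 39 (39/7 = 5.57 weeks)
- Nominal: 14 + 21 = Day 35 (5 weeks)

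**Step 3. Visit 4 counted from Visit 2.**
- Earliest: 21 − 2 = Day 19 (2.71 weeks)
- Latest: 21 + 2 = Day 23 (3.29 weeks)
- Nominal: Day 21, which matches the heading of section 8.2.3

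**Step 4. Distance between the two windows.**
- Nominal shift: 35 − 21 = 14 days
- Smallest separation: 31 − 23 = 8 days, so there is no overlap
- Earliest printed date relative to four weeks: 31 − 28 = 3 days past

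**Step 5. Would a correctly timed visit satisfy the printed window?** With both visits on time from Visit 2, the interval from Visit 3 to Visit 4 lies between 19 − 16 = 3 days and 23 − 12 = 11 days. The printed window requires 19 to 23 days. Even the longest correct interval falls short by 19 − 11 = 8 days, so every correctly timed Visit 4 misses the printed window by at least 8 days.

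**Step 6. Does the anchor touch the sample size?** No. The plan's calculation uses 60 evaluable subjects per group, a BI difference of 0.1, SD 0.17 and a two-sided 5% level. Recomputed, the power is 0.897 by the normal approximation and 0.892 by the t-test, against the stated 90%. No visit date enters that calculation.

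**The case against.** The strongest reply is that this is a self-evident typing slip with no statistical consequence. The same header says Week 3, and section 8.2.3, the summary, section 4.1, section 2.1 and every objective agree on three weeks. To schedule at Day 35, the site would have to disregard all of them, and with a single site there is no risk of different centres reading the table differently. Section 1.1 describes the table only as an overview.

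On the analysis side, SAP section 3.4 takes its timepoints from the SAP's own table, which is correct, and allows schedule deviations to be reviewed case by case at the blinded data review meeting. The primary population is m-ITT, whose definition has no window condition. Finally, the SAP was written against the protocol together with an administrative change letter of 11-Sep-2019, and its section 5 reports no departures from the two. That is consistent with the letter having corrected the anchor.

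Most of this stands, and it limits the consequence. The intent is not in doubt, a careful site would probably notice the error, and a Day 21 visit is on time under the SAP. The deviation problem is therefore confined to logging against the protocol's printed window. The objection does not make the header right. Section 8 still directs the site to that table, and no other protocol text supplies the tolerance. Whether the letter makes the correction cannot be confirmed without its contents.

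**Conclusion.** The point holds. The Visit 4 window in protocol Table 1-1 is wrong as printed: Day 31–39 on a literal reading against an intended Day 19–23, with a nominal shift of 14 days and no overlap. It should be fixed because it governs the timing of the primary-endpoint visit and because, followed literally, it would move that visit beyond the period the trial was set up to study.

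The effect goes no further than scheduling and protocol-level deviation logging. Sample size, power, the m-ITT primary analysis and the SAP's visit windows are unaffected.

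The day ranges assume that Visit 3 falls within its own stated window and that the printed anchor is taken at face value. Confidence that the printed text is wrong is high. Whether the site is still working from it depends on the administrative change letter.

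**What to change.** In protocol Table 1-1, change the anchor in the Visit 4 header from V3 to V2, so that it reads as in the SAP: "21± 2 days post V2", that is, Day 19–23. If the letter of 11-Sep-2019 already makes this correction, carry it into the protocol table so that the site has a single schedule to work from. The SAP needs no edit.

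The cost is one character in one table header, with no extra subjects, procedures or analyses.

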2 INTRODUCTION

Gingivitis is an inflammatory response to the presence of dental plaque (Kinane, 2001), which typically presents as redness, swelling (oedema) and/ or bleeding of the gums at the gingival margin surrounding the tooth. Gingivitis is a reversible condition but, if left untreated, can progress to the irreversible phase of periodontitis, where inflammation extends to the underlying tissues, periodontal ligament and alveolar bone. The resulting loss of these structures can eventually lead to tooth loss through destruction of the periodontal tissues supporting the tooth (Petersen and Ogawa, 2012). Periodontitis is reported to affect 5-20% of the world's population (Petersen and Ogawa, 2012). The maintenance of good gingival health is therefore important in preventing gingivitis and the development of periodontal disease (Chapple et al, 2015).

Dental plaque is a soft, sticky, colourless deposit of bacteria which collects on teeth and along the gingival margin; it is the causative agent of gingivitis and periodontitis (Chapple et al, 2015; Davies, 2008; Kinane, 2001; Silness and Loe, 1964; Theilade et al, 1966). Gingivitis develops when plaque elicits a local inflammatory response in the gingivae at the site of its accumulation (Davies, 2008; Marsh, 1992). Gingivitis is prevented and resolved through effective plaque control, primarily via mechanical plaque removal (i.e. toothbrushing) (Brook, 2003; Chapple et al, 2015; Davies, 2008; Marsh, 1992; Ower, 2003; Van der Weijden and Hioe, 2005).

Many people are unable to achieve adequate plaque control by toothbrushing alone. The effect of toothbrushing can be augmented by the use of dentifrice (Davies, 2008) and antimicrobial ingredients. Antimicrobial agents (such as metal salts, cetylpyridinium chloride and chlorhexidine) have been included in daily use dentifrice and mouth rinse formulations for many years, with a view to delivering improved plaque control and gum health benefits (Chapple et al, 2015). They complement mechanical plaque removal by inhibiting the growth of bacteria (via bacteriostatic and/or bactericidal activity) in areas of the mouth less accessible to the toothbrush and by interfering with the re-colonisation of plaque bacteria (Teles and Teles, 2009).

Stannous fluoride (SnF_2) is a well-known chemotherapeutic agent which has been incorporated into dentifrices since the 1940s for its oral health benefits (Makin, 2013; Miller et al, 1994; Van Loveren, 1990a; Van Loveren, 2001). The stannous ion ($\text{Sn}[\text{II}]$) is a broad-spectrum antimicrobial agent which has been shown to reduce bacterial biomass/ virulence and inhibit bacterial metabolism (Archila et al, 2004; Bellamy et al, 2012; He et al, 2012; Tinanoff, 1990; Tinanoff, 1995). $\text{Sn}[\text{II}]$ ions rapidly oxidize to "inactive" stannic ions ($\text{Sn}[\text{IV}]$) and hydrolyse to form insoluble tin compounds (for example, stannous hydroxide) in the presence of water (and saliva) and saliva-derived ions (Makin, 2013). To maximise the delivery of bioavailable $\text{Sn}[\text{II}]$ ions to the oral cavity, SnF_2 dentifrices are often "stabilized" by the addition of complexing agents or developed as low water content/anhydrous formulations.

Numerous clinical studies reported in the scientific literature demonstrate the anti-gingivitis/anti-plaque efficacy of 0.4-0.454% SnF_2 dentifrices for example, (Mallatt et al, 2007; Mankodi et al, 1997; Mankodi et al, 2005). GlaxoSmithKline Consumer Healthcare (GSKCH) has developed a 'stabilized' anhydrous 0.454% w/w SnF_2 dentifrice and confirmed its gingivitis efficacy in four clinical studies (Parkinson et al, 2014; Parkinson et al, 2015; Parkinson et al, 2018a; Parkinson et al, 2018b) in a population with mild-moderate plaque-induced gingivitis at timepoints ranging from 4 to 24 weeks.

The aim of the current clinical study is to evaluate the efficacy of a marketed 0.454% SnF_2 dentifrice (Sensodyne Repair and Protect, US market place product) in the treatment of

gingivitis (following dental prophylaxis) at earlier timepoints (over a 3-week treatment period) in a similar population. Efficacy will be compared to a negative control dentifrice.

